Overall, in the absence of randomized PMBCL clinical trials recommendations for optimal front line treatment for PMBCL subjects is more controversial than for other subtypes of DLBCL, with the consensus in US that R-CHOP followed by +/- radiotherapy or dose adjusted R-EPOCH (rituximab, etoposide phosphate, prednisone, vincristine sulfate [Oncovin], cyclophosphamide, doxorubicin hydrochloride [Hydroxydaunorubicin]) followed by +/- radiotherapy for persistent local disease are the preferred options for front line treatment.

There is currently very limited data available regarding the optimal treatment for relapsed or refractory PMBCL. The current approach is to extrapolate from modalities commonly used in the relapsed and refractory setting for other DLBCL subtypes like auto-SCT following front line or salvage chemotherapy regimens for auto-SCT ineligible subjects.

In the case of auto-SCT results from the Grupo Espanol de Linfomas y Transplante Autologo de Medula Osea (GEL-TAMO) group suggested that auto-SCT should be considered for subjects who do not achieve CR to front line treatment but who are still judged to be sensitive to chemotherapy, although in the absence of randomized clinical trials these results

continue to be controversial [38]. The GEL-TAMO group registry included 71 subjects with PMBCL who received induction chemotherapy, followed by auto-SCT as frontline therapy. At transplant, 49% of subjects were in CR, 32% in partial response/remission (PR) and 18% failed induction therapy; 53% received radiotherapy. After the transplant, 75% of subjects achieved CR. With a median follow-up of 52.5 months, the OS, PFS and disease-free survival at 4 years from diagnosis were, respectively, 84%, 81% and 81% for the first CR subjects and 49%, 42% and 82% for the induction failure (PR and refractory) subjects. Disease progression was the main cause of death (79%). Based on these results, the GEL-TAMO group concluded that subjects with PMBCL presenting at diagnosis with high-risk features or PR response to induction therapy had an encouraging survival with frontline auto-SCT. However, subjects who received the transplant after failing the induction regimen have a very poor prognosis and should be tested with other innovative approaches.

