 - a. RS subjects must also be (PET positive at screening, defined as having at least one lesion, attributable to malignancy and with appropriate correlation to anatomic imaging, with uptake greater than that of normal liver tissue.
9. Must have a performance status of 0 or 1 on the Eastern Cooperative Oncology Group (ECOG) Performance Scale.
10. Life expectancy > 3 months
11. Must demonstrate adequate organ function as defined in [Table 1](#); all screening labs should be performed within 7 days of treatment initiation. (Subjects may be enrolled based on local laboratory results pending central laboratory results.)

Table 1 Adequate Organ Function Laboratory Values

System	Laboratory Value
Hematological	
Absolute neutrophil count	PMBCL):>1,000.0/mcL/ RS:>500/mcL (unless marrow involvement) Granulocyte colony stimulating factor allowed during screening for RS only
Platelets	PMBCL \geq 75,000.0/mcL (RS: \geq 25,000/mcL) (unless marrow involvement)
Hemoglobin	\geq 8.0 g/dL (unless marrow involvement)
Renal	
Creatinine OR Measured or calculated ^a creatinine clearance (Glomerular filtration rate can also be used in place of creatinine or creatinine clearance)	\leq 1.5 X upper limit of normal (ULN) OR \geq 60.0 mL/min for subject with creatinine levels > 1.5 X institutional ULN
Hepatic	
Total bilirubin	\leq 1.5 X ULN OR Direct bilirubin \leq ULN for subjects with total bilirubin levels > 1.5 ULN
Aspartate aminotransferase (SGOT)and alanine aminotransferase (SGPT)	\leq 2.5 X ULN OR \leq 5 X ULN for subjects with liver metastasis
Albumin	\geq 3.0 g/100 mL
Coagulation	
International Normalized Ratio or Prothrombin Time (PT) Activated Partial Thromboplastin Time (aPTT)	\leq 1.5 X ULN unless subject is receiving anticoagulant therapy as long as PT or PTT is within therapeutic range of intended use of anticoagulants \leq 1.5 X ULN unless subject is receiving anticoagulant therapy as long as PT or PTT is within therapeutic range of intended use of anticoagulants
Abbreviations: PMBCL – primary mediastinal B-cell lymphoma; RS – Richter Syndrome; SGOT – serum glutamate oxaloacetic transaminase; SGPT – serum glutamate pyruvic transaminase. ^a Creatinine clearance should be calculated per institutional standard.	

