5.8 Subject Withdrawal/Discontinuation Criteria

5.8.1 Discontinuation of Treatment

Discontinuation of treatment does not represent withdrawal from the trial.

As certain data on clinical events beyond treatment discontinuation are important to the study, they must be collected through the subject's last scheduled follow-up, even if the subject has discontinued treatment. Therefore, all subjects who discontinue trial treatment prior to completion of the treatment period will still continue to participate in the trial as specified in Section 6.0 - Trial Flow Chart and Section 7.1.5.3 – Post Treatment Visits.

Subjects may discontinue treatment at any time for any reason or be dropped from treatment at the discretion of the investigator should any untoward effect occur. In addition, a subject may be discontinued from treatment by the investigator or the Sponsor if treatment is inappropriate, the trial plan is violated, or for administrative and/or other safety reasons. Specific details regarding procedures to be performed at treatment discontinuation are provided in Section 7.1.4 – Other Procedures.

A subject must be discontinued from treatment but continue to be monitored in the trial for any of the following reasons:

- The subject or subject's legally acceptable representative requests to discontinue treatment.
 - Confirmed radiographic disease progression outlined in Section 7.1.2.7.5 (exception if the Sponsor approves treatment continuation).
 - Unacceptable adverse experiences as described in Section 7.2
 - Any progression or recurrence of any malignancy, or any occurrence of another malignancy that requires active treatment
 - Intercurrent illness other than another malignancy as noted above that prevents further administration of treatment
 - Recurrent Grade 2 pneumonitis
 - A confirmed positive serum pregnancy test
 - Noncompliance with trial treatment or procedure requirements
 - Investigator's decision to withdraw the subject

For subjects who are discontinued from treatment but continue to be monitored in the trial, all visits and procedures, as outlined in the trial flowchart, should be completed.

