7.1.2.7 Assessment of Disease and Tumor Imaging

7.1.2.7.1 Tumor Imaging and Criteria for Assessment of Disease

The process for image collection and transmission to the independent central imaging vendor can be found in the Site Imaging Manual. Independent central review based on IWG response criteria (Cheson, 2007 [1]) will be used to determine subject eligibility.

The central imaging vendor will receive all CT/PET images from the sites including baseline images and will confirm eligibility. **Eligibility will be based on the independent central review assessment, rather than site assessment. Expedited confirmation of measurable disease as determined by central review will be communicated to the site.**

Anti-tumor activity of pembrolizumab by CT/PET will be evaluated using the following criteria:

- PMBCL: IWG response criteria (Cheson, 2007 [1]) See Section 12.7.
- RS: IWG response criteria (Cheson, 2007 [1]) with special considerations for RS (Section 12.7). In subjects with rrRS, assessment of disease in the bone marrow will be limited to RS lymphoma.

The IWG will be applied by the independent central imaging vendor as the primary measure for eligibility, assessment of tumor response, and date of disease progression. CT/PET imaging showing subject's eligibility should be submitted to the central imaging vendor immediately. The site will be notified if the independent central review confirms eligibility. Additionally, the investigator will apply the IWG response criteria for assessment of disease response and disease progression. In addition, assessment of lymphoma B symptoms should occur with each lymphoma disease response assessment.

In subjects with RS, assessment of disease in the bone marrow will distinguish changes due to RS or transformed lymphoma from changes due to the pre-existing CLL. RS subjects may be assessed as showing radiographic CR if all lesions resolve on anatomic imaging, or if all remaining lesions show PET avidity lower than normal liver tissue, consistent with complete disappearance of fluorodeoxyglucose (FDG)-avid disease. If radiographic CR is observed (no evidence of active disease on imaging), a final response determination of CR requires marrow clearance of RS (as determined by marrow biopsy and aspirate), as well as

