8.5 Analysis Population

8.5.1 Efficacy Analysis Population

The analysis of primary efficacy endpoints are based on the All Subjects as Treated (ASaT) population, i.e., subjects will be included if they receive at least one dose of study medication (pembrolizumab).

Supportive analyses will be conducted in the Full Analysis Set (FAS) population, which consists of all subjects who 1) receive at least one dose of study medication; 2) have a baseline disease assessment, and 3) have a post baseline disease assessment or discontinue the trial due to PD/drug related AE.

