8.6.1.1 Objective Response Rate

The primary efficacy endpoint for this study is the ORR for each cohort, defined as the proportion of subjects who have response (CR or PR) prior to disease progression. In the rrPMBCL cohort, an exact binomial test will be conducted versus a fixed control rate. In both cohorts, the final analysis for the primary endpoint will be conducted when the last subject has reached the Week 12 response assessment or has discontinued study therapy.

The analysis will consist of the point estimate and 95% (90% for rrRS cohort) 2-sided exact CI using the Clopper-Pearson method which will have at least 95% (90% for rrRS cohort) coverage of the true rate.

Since an investigator may still continue to treat subjects with pembrolizumab who have progressed according to IWG criteria, exploratory analyses (point estimate and 90% 2-sided exact confidence interval) will be conducted for ORR to consider these subjects who later achieve PR or CR post-progression as responders. An additional exploratory analysis for ORR will be conducted based on the Lugano classification (Cheson, 2014 [2]).

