8.6.1.3 Progression-Free Survival

The non-parametric Kaplan-Meier method will be used to estimate the PFS curve.

Since disease progression is assessed periodically, PD can occur any time in the time interval between the last assessment where PD was not documented and the assessment when PD is documented. For the primary analysis, for the subjects who have PD, the true date of disease progression will be approximated by the date of the first assessment at which PD is objectively documented per IWG criteria, regardless of discontinuation of study drug. Death is always considered as a confirmed PD event.

In order to evaluate the robustness of the PFS endpoint, we will perform two sensitivity analyses with a different set of censoring rules. The first sensitivity analysis is the same as the primary analysis except that it censors at the last disease assessment without PD when PD or death is documented after more than one missed disease assessment. The second sensitivity analysis is the same as the primary analysis except that it considers discontinuation of treatment or initiation of new anticancer treatment, whichever occurs later, to be a PD event for subjects without documented PD or death. The censoring rules for primary and sensitivity analyses are summarized in [Table 9](#).

Table 9 Censoring rules for Primary and Sensitivity Analyses of Progression-Free Survival

Situation	Primary Analysis	Sensitivity Analysis 1	Sensitivity Analysis 2
No progressive disease (PD) and no death; new anticancer treatment is not initiated	Censored at last disease assessment	Censored at last disease assessment	Censored at last disease assessment
No PD and no death; new anticancer treatment is initiated	Censored at last disease assessment before new anticancer treatment	Censored at last disease assessment before new anticancer treatment	Progressed at date of new anticancer treatment
PD or death documented after ≤ 1 missed disease assessment	Progressed at date of documented PD or death	Progressed at date of documented PD or death	Progressed at date of documented PD or death
PD or death documented after ≥ 2 missed disease assessments	Progressed at date of documented PD or death	Censored at last disease assessment prior to the ≥ 2 missed disease assessment	Progressed at date of documented PD or death

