8.6.1.5 Overall Survival

The median OS, if reached, will be estimated in the given analysis population. In addition, the Kaplan-Meier method will be used to estimate the survival curve.

Table 10 Efficacy Analysis Methods for Primary and Secondary Efficacy Endpoints

Endpoint/Variable	Statistical Method	Analysis Population	Missing Data Approach
Primary:			
Objective Response Rate (ORR) 
 Central review 	rrPMBCL: Exact test of binomial parameter; Point Estimate and 2-sided 95% exact CI rrRS: Point estimate and 2-sided 90% exact CI	ASaT/FAS	Subjects with missing data are considered non-responders
Secondary:			
Objective Response Rate (ORR) 
 Investigator Assessment 	Point estimate; 2-sided 90% exact CI	ASaT/FAS	Subjects with missing data are considered non-responders
Progression-free survival (PFS) 
 Central review Investigator assessment 	Summary statistics using Kaplan-Meier method	ASaT/FAS	Censored at last assessment (see Table 9 for sensitivity analyses based on alternative censoring)
Duration of Response (DOR) 
 Central review Investigator assessment 	Summary statistics using Kaplan-Meier method	All responders	Non-responders are excluded in analysis
Disease Control Rate (DCR) 
 Central review Investigator assessment 	Point Estimate; 2-sided 90% exact CI	ASaT/FAS	Subjects with missing data are considered non-responders
Overall survival (OS)	Summary statistics using Kaplan-Meier method	ASaT/FAS	Censored at last assessment
Abbreviations: ASaT – All Subjects as Treated; CI – confidence interval; FAS – Full Analysis Set; rrPMBCL – relapsed or refractory primary mediastinal B-cell lymphoma; rrRS – relapsed or refractory Richter Syndrome;			

For the rrPMBCL cohort, efficacy updates for the parameters in the above table will be conducted using a data cut-off based on when the last subject remaining on study has completed approximately 9 months and 12 months of efficacy assessments and then at 2 years after the last subject initiated treatment, which corresponds to the end of the protocol-specified treatment period. No formal statistical testing is planned. Subsequent yearly analyses will be conducted (i.e., 3 years after the last subject initiated treatment, etc.) until the trial is complete, including follow-up information on subjects who enter the re-treatment period.

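### Does the Full Analysis Set rule, which drops some unassessed treated subjects by reason for leaving, need to be rewritten?

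*Combined protocol and SAP*

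**What the plan says.** Section 8.5.1 bases the primary efficacy analysis on the ASaT, meaning every subject given at least one dose. The FAS is for supportive analyses. It requires a dose, a baseline disease assessment and, third, that subjects "have a post baseline disease assessment or discontinue the trial due to PD/drug related AE".

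Table 10 (after section 8.6.1.5) names both populations for ORR, DCR, PFS and OS. For ORR and DCR its missing-data rule is "Subjects with missing data are considered non-responders".

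Three other places bear on how the third criterion is read:

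- Section 8.6.1.3 (PFS): "Death is always considered as a confirmed PD event".
- Section 5.8.1: "Discontinuation of treatment does not represent withdrawal from the trial".
- Section 8.6.1.1: the final ORR analysis is run "when the last subject has reached the Week 12 response assessment or has discontinued study therapy".

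The second criterion should remove nobody. Inclusion criterion 8 requires measurable disease by central review, and section 7.1.2.7.1 adds: "Eligibility will be based on the independent central review assessment, rather than site assessment". In practice the third criterion alone separates the FAS from the ASaT.

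**The concern.** FAS membership depends on what happens after the first dose and on the reason recorded for leaving. An unscanned subject who leaves because of progression or a drug-related event stays in. One who leaves because of intercurrent illness, an unrelated event or personal choice drops out. Each subject dropped is a non-responder in the ASaT, so the supportive ORR and DCR can only match or exceed the primary ones. A supportive analysis that cannot come out worse is no test of robustness.

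The wording is also loose in two ways. It does not mention death, and the first scheduled scan is at Week 12, so a death before any assessment is possible. The PFS rule on death might carry over, but section 8.5.1 does not refer to it. And the criterion speaks of discontinuing the trial, whereas section 5.8.1 keeps subjects in the trial after treatment stops. Read literally, an unscanned subject who stops treatment for progression and enters survival follow-up would not qualify. Two programmers could build different sets.

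At stake would be flattering supportive ORR and DCR, and higher FAS curves for PFS and OS if early deaths were left out.

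**Working it through.** **The plan's own figures.** Inputs from sections 8.7 and 8.8: N = 50, control rate 15%, alternative 35%, bounds of 11/30 (interim) and 14/50 (final). Exact binomial tails:

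- P(X ≥ 14 | 50, 0.15) = 0.0132, as in Table 11.
- P(X ≥ 11 | 30, 0.15) = 0.0029, as in Table 11.
- P(X ≥ 14 | 50, 0.35) = 0.884, matching the stated power of at least 88%.

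All use the ASaT count, so the FAS definition does not enter them.

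**Direction.** Let x be responders and k the treated subjects removed by the third criterion. They have no post-baseline assessment, so none is among the x. ASaT ORR = x/50 and FAS ORR = x/(50 − k). The difference is x·k/[50(50 − k)], which is at least 0 and equals 0 when k = 0. The same holds for DCR.

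**Size for ORR.** The documents do not give k, so the values below are assumptions. With x = 14 and 95% Clopper-Pearson intervals:

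| k | ORR | 95% CI |
|---|---|---|
| 0 | 14/50 = 28.0% | 16.2% to 42.5% |
| 1 | 14/49 = 28.6% | 16.6% to 43.3% |
| 3 | 14/47 = 29.8% | 17.3% to 44.9% |
| 5 | 14/45 = 31.1% | 18.2% to 46.6% |

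The interval at k = 0 is 42.5 − 16.2 = 26.3 points wide. One removal moves the estimate by 0.6 points and five by 3.1. For an assumed DCR of 25/50 = 50.0%, k = 1 gives 25/49 = 51.0% and k = 5 gives 25/45 = 55.6%.

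**How large k can be.** The flow chart in section 6.1 schedules imaging at discontinuation (footnote d waives it only if a scan was done in the previous 4 weeks). Section 7.1.2.7.4 allows an earlier first scan on clinical progression. Section 7.1.4.1 asks for the final-visit activities at discontinuation. Section 7.1.5.4 puts subjects who stop for reasons other than confirmed progression into 12-weekly disease assessment. Most who stop early should therefore acquire an assessment and stay in the FAS. What remains is early deaths before a scan, refusals, losses, and subjects who start other therapy unscanned.

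**PFS and OS.** If the death rule in section 8.6.1.3 governs, no early death is excluded and there is no effect from deaths. Otherwise let f be the fraction of deaths before Week 12 that is excluded, and assume exponential OS with median m:

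- t₀ = 84/30.4375 = 2.76 months
- d = 1 − exp(−ln2·t₀/m)
- FAS median = m·[1 − log₂(1 − f·d)]

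For m = 9, d = 19.1%. Then f = 0.10 excludes 50 × 0.10 × 0.191 = 0.96 subjects and gives 9.25 months. Both m and f are assumptions. The entry criterion "Life expectancy > 3 months" suggests that a constant hazard overstates early deaths. The registry in section 4.2.1.1, where 79% of deaths were from progression, concerns frontline transplant, so it sets no limit on f here.

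**What a rewrite would do.** Suppose the FAS admitted anyone assessed, or who had reached Week 12, or who had died or stopped treatment before it. By the time of the final ORR analysis every treated subject meets one of these conditions. So k = 0, apart from any failure of the baseline criterion, and the FAS becomes the ASaT.

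**The case for a change.** The strongest case for a change is that the protocol already has a better rule. Section 8.7 counts a subject as evaluable once Week 12 is reached or therapy has stopped before it, for any reason. Aligning section 8.5.1 with that costs only wording. Table 10 also pairs the exact test with both populations, so a near miss could look better in the FAS. With 13 responders, 13/50 = 26.0% has one-sided p = 0.0301 and misses the 0.0132 bound. 13/46 gives 0.0153 and still misses, but 13/45 = 28.9% gives 0.0127. In the Richter cohort, closed after 24 subjects, the relative inflation k/(n − k) is larger for the same k.

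The arithmetic stands, and so does the reading of it: FAS rates should not be presented as an independent check on the ASaT rates. The rest has less force. The crossing needs five unassessed exclusions, 10% of the cohort, and the decision still rests on 13/50. The Richter cohort has no hypothesis test. The trial-versus-treatment slip affects few subjects: progression is usually documented on a scan, which satisfies the criterion anyway, and since section 7.1.5.4.2 sends progressing subjects to survival follow-up, stopping treatment is plainly what is meant. How unscanned deaths are classed is a real gap, but one an analyst can settle when programming the set. Section 8.0 provides a supplemental plan for changes to non-confirmatory analyses, and section 8.6.3.1 already reports reasons for discontinuation.

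**Conclusion.** No change to the plan is needed. An evaluable-type supportive set yields rates at or above the all-treated rates by construction, and the plan labels it supportive and reports the ASaT results alongside. The primary test, the 11/30 and 14/50 bounds and the 88% power are untouched.

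The likely size is 0.6 points of ORR per excluded subject when there are 14 responders, and possibly nothing. This rests on k being small, which the imaging rules support but the documents do not quantify. The survival illustration rests wholly on assumed values, and the effect of early deaths vanishes if the PFS rule on death is applied.

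A rule neutral as to reason would merge the FAS with the ASaT by the final analysis, and dropping FAS PFS and OS would only delete a secondary presentation. What is left is loose wording on unscanned deaths and on trial versus treatment, which analysts can resolve sensibly and which alters no planned conclusion.

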8.5.2 Safety Analysis Population

The ASaT population will be used for the analysis of safety data in this study. The ASaT population consists of all enrolled subjects who received at least 1 dose of study treatment (pembrolizumab). At least one laboratory or vital sign measurement obtained subsequent to at least one dose of trial treatment is required for inclusion in the analysis of each specific parameter. To assess change from baseline, a baseline measurement is also required.

